9.2 Outcome Measures

NOTE: Due to insufficient numbers of resting CD4+ T-cells available from some Cohort 4 participants to perform all the planned assays (e.g., cell-associated HIV-1 RNA, total HIV-1 DNA, histone acetylation, PTEF-b activation), those assays will be performed using peripheral blood mononuclear cells (PBMCs). The team carefully reassessed the priorities for the use of these cells based on advances in the field since the prior protocol version. Accordingly, the relevant objectives and outcomes measures sections have been updated.

- 9.2.1 Primary Endpoints
 - 9.2.1.1 Safety

Occurrence of Grade \geq 3 AE including signs/symptoms, lab toxicities, and /or clinical events that is probably, possibly or definitely related to study treatment (as judged by the core team, blinded to treatment arm) any time from the time of study treatment administration until 28 days after the administration.

- 9.2.1.2 Efficacy
 - 9.2.1.2.1 Change in plasma HIV-1 RNA levels from baseline (average of pre-entry and entry values) as detected by single copy assay at 24 and 48 hours (average) after the single administration of RMD or placebo in Cohorts 1 3.
 - 9.2.1.2.2 Change in plasma HIV-1 RNA levels from baseline (average of pre-entry and entry values) as detected by single copy assay before and 24 hours after each administration of RMD or placebo in Cohort 4.
 - 9.2.1.2.3 Change in cell-associated HIV-1 RNA levels in resting CD4+ T-cells from baseline to 24 hours after the single administration of RMD or placebo in Cohorts 1 – 3.
 - 9.2.1.2.4 Change in cell-associated HIV-1 RNA levels in **PBMCs** before and **24 hours** after each administration of RMD or placebo in Cohort 4.
- 9.2.2 Secondary Outcome Measures
 - 9.2.2.1 Changes in plasma HIV-1 RNA levels as detected by single copy assay from baseline to after the single administration of RMD or placebo in Cohorts 1 3 and after each administration of RMD or placebo in Cohort 4.

- 9.2.2.2 Change in cell-associated HIV-1 RNA levels in resting CD4+ T-cells from baseline to 14 days after the administration of RMD or placebo in Cohorts 1-3, and in PBMCs after each administration of RMD or placebo in Cohort 4.
- 9.2.2.3 Changes in histone acetylation in CD4+ **and CD8+** T-cells from baseline to after the single administration of RMD or placebo in Cohorts 1-3 and after each administration of RMD or placebo in Cohort 4.
- 9.2.2.4 Changes in total HIV-1 DNA in resting or total CD4+ T-cells from baseline to after the single administration of RMD or placebo in Cohorts 1 3 and in PBMCs after each administration of RMD or placebo in Cohort 4.
- 9.2.2.5 Pharmacokinetic parameters for RMD and co-administered antiretroviral drugs (EFV, DTG, or RAL).
- 9.2.2.6 Number/percent of participants in Cohorts 1 3 with HIV-1 RNA levels ≥200 copies at the Day 7 visit
- 9.2.2.7 Number/percent of participants in Cohort 4 with HIV-1 RNA levels ≥200 copies/mL at scheduled post-infusion 4 visits.
- 9.2.2.8 All reported Grade 2-4 AEs.
- 9.2.2.9 Change in CD4+ T cell percent from baseline to after each administration of RMD or placebo in Cohort 4.
- 9.2.2.10 Change in CD4+ and CD8+ T cell percent from baseline to after the single administration of RMD or placebo in Cohorts 1 3 and after each administration of RMD or placebo in Cohort 4.
- 9.2.2.11 Changes in the percentage of CD3+ CD4+ and CD3+ CD8+ lymphocytes and cellular markers of immune activation (CD38/HLA-DR or CD69/CD25 expression on CD4+ and CD8+ Tcells) from baseline to after the single administration of RMD or placebo in Cohorts 1 – 3 and after each administration of RMD or placebo in Cohort 4.
- 9.2.2.12 Change in percentage of total lymphocytes expressing annexin V and/or 7 amino-actinomycin D (7-AAD) from baseline to after the single administration of RMD or placebo in Cohorts 1 – 3 and after each administration of RMD or placebo in Cohort 4.
- 9.2.2.13 Changes in P-TEFb and HIV-1 expression; changes in PTEF-b phosphorylation in CD4+ and CD8+ T-cells from baseline to after

the single administration of RMD or placebo in Cohorts 1 - 3 and after each administration of RMD or placebo in Cohort 4.

9.2.3 Exploratory Outcome Measures

9.2.3.1 Change in quantitative viral outgrowth assay (qVOA) from baseline to after administration of all doses of RMD or placebo in Cohort 4.

- 9.2.3.2 Changes in proportion of cycling CD4+ and CD8+ T-cells (Ki67 expression) from baseline to after the single administration of RMD or placebo in Cohorts 1 3 and after each administration of RMD or placebo in Cohort 4.
- 9.2.3.3 Changes in the levels of soluble markers IL-6, C-reactive protein (CRP), and D-dimer from baseline to after the single administration of RMD or placebo in Cohorts 1 3 and after each administration of RMD or placebo in Cohort 4.
- 9.2.3.4 Changes in HIV-specific immune responses from baseline to after the first and fourth administration of RMD or placebo in Cohort 4.
- 9.2.3.5 Changes in host RNA expression profiles by RNAseq of PBMC from after the first and fourth administration of RMD or placebo in Cohort 4.
- 9.3 Randomization and Stratification

Each cohort will open sequentially. Within each cohort, 15 participants will be randomized to receive RMD (12 participants) or placebo (3 participants). Randomization will use a permuted block method without institutional balancing or stratification. After each cohort enrollment is complete, study enrollment will be suspended until a decision on the subsequent cohort is made, based on the dose escalation criteria.

9.4 Sample Size and Accrual

The total sample size of this study will be 60 evaluable participants (12 evaluable active plus 3 evaluable placebo controls, per dosing cohort) if all four cohorts are enrolled. For Cohorts 1 - 3, participants who do not receive study drug (RMD or placebo) and/or complete the pre-infusion blood collection and/or the 24-hour blood collection will be replaced. For Cohort 4, participants who do not complete all 4 doses of study drug (RMD or placebo) and/or placebo) and/or who miss more than one of the 24-hour post-infusion blood collection will be replaced.

9.4.1 Safety

Dose escalation criteria for consideration by the SMC are defined as:

- a) No more than three participants have experienced a Grade 3 AE that is probably or possibly related to study treatment (as judged by the core team, blinded to treatment arm) prior to or on Day 14 after the treatment administration; and
- b) None of the participants has experienced a Grade ≥ 3 AE that is definitely related to study treatment or that is Grade ≥ 4 and probably or possibly related to study treatment (as judged by the core team, blinded to treatment arm) prior to or on Day 14 after the treatment administration.

Note: The occurrence of a Grade 3 infusion site pain or tenderness that is sustained for less than 48 hours will be excluded from the dose escalation evaluation.

The tables below show the probabilities of dose escalation under various assumed true rates for two types of AEs as described above and under various enrollment projections (i.e., if at least 12 but fewer than 15 participants are enrolled into a cohort).

In the tables, the column "True rate of Grade 3 AE probably or possibly related to study Rx" is the probability conditional on not having the "Grade 3 or higher AE definitely related or Grade 4 or higher AE probably or possibly related to study Rx". The column "True rate of Grade 3 or higher AE definitely related or Grade 4 or higher AE probably or possibly related to study Rx" is the unconditional probability of the event. The calculations in these tables assume there is negligible probability that a participant in the placebo arm will experience a Grade \geq 3 AE.

The proposed sample size provides a reasonably high probability of dose escalation when the true event rates are, in fact, acceptable. For example, if the probability of a participant in the active treatment arm of a given dose cohort experiencing a Grade 3 AE as described above that is possibly or probably due to study treatment is 0.012 (ie, 1.2%), and the corresponding probability of experiencing such an AE that is definitely due to study treatment is 0.10 (ie, 1%), then the probability that the study will dose escalate to the next higher dose is 0.89 (ie, 89%). Given that this is an acceptable safety profile, this means that the probability of incorrectly concluding the current dose unsafe is 11%. On the other hand, the proposed sample size provides a low probability of dose escalation when the true event rates are unacceptable. For example, if the true rate of Grade 3 AE that is probably or possibly related to study treatment is 0.180 (ie, 18%), and the true rate of Grade 3 AE that is definitely related or Grade 4 or higher AE that is probably or possibly related to study treatment is 0.150 (ie, 15%), then the probability of dose escalation is only 0.12 (ie, 12%), and the corresponding probability of not dose escalating and correctly concluding the dose unsafe is high at 0.88 (1-0.12).

Table 9.4.1-1:	Probabilities of dose escalation under various assumed true rates	
(n=12 on RMD	l.	

True rate of Grade 3 AE probably or possibly related to study Rx	True rate of Grade 3 or higher AE definitely related or Grade 4 or higher AE probably or possibly related to study Rx	Probability of Dose Escalation
0.006	0.005	0.94
0.012	0.010	0.89
0.024	0.020	0.78
0.036	0.030	0.69
0.048	0.040	0.61
0.060	0.050	0.54
0.120	0.100	0.27
0.180	0.150	0.12
0.240	0.200	0.05
0.360	0.300	<0.01

The randomization of study participants to either RMD or placebo uses a permuted block design. With a ratio of 4:1, a block size of 5 has been used. Based on this method, with a total of 12 participants enrolled in Cohort 3, there will be 9 or 10 participants randomized to receive RMD. The following calculations of probabilities of dose escalation using the same criteria are based on N=9 or 10 on RMD.

Table **9.4.1-2**: Probability of dose escalation under various assumed true rates (n=10 on RMD)

True rate of Grade 3 AE probably or possibly related to study Rx	True rate of Grade 3 or higher AE definitely related or Grade 4 or higher AE probably or possibly related to study Rx	Probability of Dose Escalation
0.006	0.005	0.95
0.012	0.010	0.90
0.024	0.020	0.82
0.036	0.030	0.74
0.048	0.040	0.66
0.060	0.050	0.60
0.120	0.100	0.34
0.180	0.150	0.18
0.240	0.200	0.09
0.360	0.300	0.01

With N=10, the study still provides a low probability (although higher than with N=12) of dose escalation when the true event rates are unacceptable. For example, for the same assumed rates as above, the probability of dose escalation is 0.18 (ie, 18%) vs. 0.12 with N=12, and the corresponding probability of not dose escalating and correctly concluding the dose unsafe is high at 0.82 (1-0.18) vs. 0.88.

Table **9.4.1-3:** Probability of dose escalation under various assumed true rates (n=9 on RMD)

True rate of Grade 3 AE probably or possibly related to study Rx	True rate of Grade 3 or higher AE definitely related or Grade 4 or higher AE probably or possibly related to study Rx	Probability of Dose Escalation
0.006	0.005	0.96
0.012	0.010	0.91
0.024	0.020	0.83
0.036	0.030	0.76
0.048	0.040	0.69
0.060	0.050	0.63
0.120	0.100	0.38
0.180	0.150	0.22
0.240	0.200	0.11
0.360	0.300	0.02

With N=9, the probabilities of dose escalation are larger than in the setting with N=12 as expected. For example, for the same assumed rates as above, the probability of dose escalation is 0.22 (ie, 22%) vs. 0.12 with N=12, and the corresponding probability of not dose escalating and correctly concluding the dose unsafe is high at 0.78 (1-0.22) vs. 0.88.

9.4.2 Efficacy

For evaluating primary efficacy endpoints in Cohorts 1 - 3, the study will use the results from the placebo arms combined across Cohorts 1 - 3 as a control. If all three cohorts are fully enrolled and treated and followed per protocol, there will be n=9 participants in the combined placebo control group and n=36 participants in the combined RMD group.

The study is powered on the change of HIV-1 RNA by SCA from baseline (average of pre-entry and entry values) to the 24 and 48 hour measurements (averaged) after RMD administration. Under the assumptions that the standard deviation of log_{10} change is 0.32 (derived from A5244 SCA measurements) and there will be no change in HIV-1 RNA in the placebo group, with a sample size of n=36 in the combined RMD group and n=9 in the combined placebo group, the study will have 80% power to detect a 0.42 log_{10} increase in HIV-1 RNA by SCA using a two-sided Wilcoxon rank sum test at 5% level.

For the secondary comparison of a given RMD dose group (n=12) with the combined placebo group (n=9), the study will have 80% power to detect a 0.52 log_{10} increase in RNA by SCA.

The sample size estimation includes an adjustment of 15% for the potential loss of efficiency due to left censoring of SCA results below assay limit.

The following table presents the detectable effect size based on various sample sizes and standard deviations:

Estimated standard deviation of log ₁₀ change	Sample size per cohort: RMD/ placebo	Detectable Effect size (log ₁₀) with 80% power for comparison between combined RMD group and combined placebo group	Detectable Effect size (log ₁₀) with 80% power for comparison between a given RMD dose group and combined placebo group
SD=0.29	15/5	0.29	0.37
	12/3	0.38	0.47
SD=0.32	15/5	0.32	0.41
	12/3	0.42	0.52
SD=0.35	15/5	0.35	0.44
	12/3	0.46	0.56

Table **9.4**.**2-1**: Detectable effect sizes based on various sample sizes and assumed standard deviations.

For comparison of the change of cell-associated viral RNA in resting CD4+ Tcells from baseline, assuming that the standard deviation (SD) of log_{10} change is 0.33 [39] and there will be no change in HIV-1 RNA in the placebo group, with 36 active and 9 placebos combined in Cohorts 1 – 3, the study will have 80% power to detect a difference of 0.38 log_{10} copies/million CD4 cells in the cell-associated viral RNA between the two combined groups, using a two-sided 5% level Wilcoxon rank sum test. For Cohort 4, with 12 in the RMD group and 3 in the placebo group, the study will have 80% power to detect a difference of 0.79 log_{10} copies/million CD4 cells.

For Cohort 4, a quantitative viral outgrowth assay (qVOA) will be performed instead of the modified TVR assay [41]. The team opted to perform the qVOA

since it is the current gold-standard assay for quantifying the latent reservoir.

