7.13 Cohort 4 primary efficacy outcomes

7.13.1 Change in plasma HIV-1 RNA levels from baseline (average of pre-entry and entry values) as detected by single copy assay before and 24 hours after each administration of RMD or placebo in Cohort 4.

The analysis of 7.13.1 will be combined with 7.14.1. The available timepoints are: pre-entry (-35 to -28 days), pre- & 24hr post-infusion for all 4 infusions, and 72hr post-2nd-infusion

SCA values below the limit of detection (LOD) will be imputed as equal to half the limit of detection (i.e., if LOD=0.4 copies/mL, results < 0.4 copies/mL will be imputed as 0.2 copies/mL).

a. Tables:

- Completeness of data for all measurement time points
- N (%) of SCA value < LOD at all measurement time points
- Baseline SCA: N, median, 25th and 75th percentiles, min, max
- Pre- and 24hr post-infusion SCA for each infusion and 72hr post-2nd-infusion: N, median, 25th and 75th percentiles, min, max
- Change (at each post-entry time point baseline) SCA: N, median, 25th and 75th percentiles, min, max
- Change (post-infusion time point pre-infusion time point for each infusion) SCA: N, median, 25th and 75th percentiles, min, max

NOTE: Baseline averages will be calculated using log10-transformed SCA values.

Wilcoxon rank sum test will be used for the comparison between groups. Wilcoxon signed rank test will be used to test within-group changes for RMD group. Two-sided 95% confidence intervals for the shift will be calculated based on Hodges-Lehmann estimator.

b. Figure:

- Longitudinal median (Q1, Q3) plots for all measurement time points by RMD and placebo.
- Longitudinal, participant-specific, (spaghetti) plots for all measurement time points with open symbol for values below the LOD and different symbols/colors for RMD and placebo.

7.13.2 Change in cell-associated HIV-1 RNA levels in PBMCs before and 24 hours after each administration of RMD or placebo in Cohort 4.

The analysis of 7.13.2 will be combined with 7.14.2. The available timepoints are the same as 7.13.1 and 7.14.1. The same analysis approach will be used as in 7.13.1 (except N (%) below LOD).

NOTE: Cell-associated RNA results below the detection limit are imputed with 1 copy/million PBMCs.

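### Cohort 4's 0.79 log10 is not the 80% power point of the rank-sum test named in Protocol 9.4.2, and the SAP leaves the 12 v 3 p-value rule open

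*Protocol*

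**What the plan says.** Protocol 9.4.2 first treats Cohorts 1-3 combined (36 romidepsin v 9 placebo). It takes an SD of log10 change of 0.33 for cell-associated RNA in resting CD4+ T-cells and assumes that "there will be no change in HIV-1 RNA in the placebo group". It then states that "the study will have 80% power to detect a difference of 0.38 log_{10} copies/million CD4 cells", with the comparison made "using a two-sided 5% level Wilcoxon rank sum test". The next sentence carries this to the multiple-dose cohort, at 12 romidepsin v 3 placebo, and gives the result as follows: "the study will have 80% power to detect a difference of 0.79 log_{10} copies/million CD4 cells". No separate SD, software, approximation or allowance is given for that second figure. The 15% allowance earlier in the section is worded as "an adjustment of 15% for the potential loss of efficiency due to left censoring of SCA results", which is the plasma single-copy assay and not cell-associated RNA.

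On analysis, Protocol 9.6 says that Cohort 4 uses the same approach as Cohorts 1-3, a rank-sum test. SAP 7.13.1 says "Wilcoxon rank sum test will be used for the comparison between groups", adds 95% intervals based on the Hodges-Lehmann estimator, and 7.13.2 adopts the same approach for cell-associated RNA. Neither document says whether p-values or intervals are exact or asymptotic. SAP 7.13.2 imputes results below the limit to a single value, 1 copy per million PBMCs, and gives no tie rule.

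**The concern.** The 0.79 is the only numerical power statement for Cohort 4, and it concerns one of that cohort's primary efficacy endpoints. A reader should be able to recover it from the SD, group sizes and test printed beside it, and cannot.

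The second issue affects the analysis itself. With 3 placebo participants the rank-sum statistic takes few values in the tail, so the exact, normal and t reference distributions give different rejection regions. SAP 6.7 requires the primary analyses to be validated by independent coding. Two correct programs with different p-value options could disagree about significance on the same data.

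**Working it through.** **Inputs.** From Protocol 9.4.2: 12 v 3; SD 0.33; no placebo change; two-sided 5% rank sum. Assumptions: a normal shift, no ties, and the resting CD4+ T-cell SD carrying over to the Cohort 4 PBMC endpoint, for which no SD is given.

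**Companion figure first (36 v 9, stated 0.38).** The exact rank-sum test reaches 80.4% power at 0.37 and 82.4% at 0.38. Across p-value rules the 80% point is 0.37 to 0.38, so this figure is close to what the named test gives.

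**Null distribution for 12 v 3.** There are C(15,3) = 455 arrangements. The counts for U = 0, 1, 2, 3, 4, 5 are 1, 1, 2, 3, 4, 5. Two-sided exact p-values:
- U = 2: 2 × 4/455 = 0.018
- U = 3: 2 × 7/455 = 0.031
- U = 4: 2 × 11/455 = 0.048
- U = 5: 2 × 16/455 = 0.070

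The exact test therefore rejects at U ≤ 4 or, by symmetry, U ≥ 32.

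**Approximations.** The mean of U is 12 × 3/2 = 18 and its variance is 12 × 3 × 16/12 = 48, so its SD is 6.928.
- Normal, uncorrected, U = 4: z = 14/6.928 = 2.021, p = 0.043. At U = 5, z = 13/6.928 = 1.876, p = 0.061. It has the same rejection region as the exact test.
- Normal, continuity-corrected, U = 4: z = 13.5/6.928 = 1.949, p = 0.051. At U = 3, z = 14.5/6.928 = 2.093, p = 0.036. It rejects only at U ≤ 3.
- Continuity-corrected value referred to t with 14 df: p = 0.055 at U = 3 and 0.042 at U = 2. It rejects only at U ≤ 2.

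**Power** (simulation, at least 1 million replicates, shift/0.33):

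| p-value rule | Rejects at | True size | Power at 0.70 | Power at 0.79 | 80% point |
|---|---|---|---|---|---|
| Exact, or uncorrected normal | U ≤ 4 | 0.048 | 81% | 88.9% | 0.69 |
| Continuity-corrected normal | U ≤ 3 | 0.031 | 74% | 83.5% | 0.75 |
| Continuity-corrected t | U ≤ 2 | 0.018 | 64% | 75.7% | 0.83 |

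The stated pair, 0.79 and 80%, matches none of the rows. On the fold scale, 0.69 log10 is about 4.9-fold and 0.79 about 6.2-fold.

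**Where 0.79 might come from.** A t-test with all 15 participants gives 0.65, which does not match. These unstated recipes come near:
- A t-test on sizes reduced by 10% and truncated: 12 v 3 becomes 10 v 2, giving 0.795; 36 v 9 becomes 32 v 8, giving 0.375.
- A t-test on sizes scaled by 3/π and truncated: 11 v 2 gives 0.781; 34 v 8 gives 0.372.
- The exact result inflated by 15%: 0.692 × 1.15 = 0.796. The same step on the companion gives 0.37 × 1.15 = 0.43, not 0.38.

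**Sensitivity.** With other error shapes, exact-test power at 0.79 stayed at 89-90%. An SD of about 0.38 would make 0.79 roughly the exact-test 80% point (79.3%), but the documents give no such SD.

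**The case against.** The strongest reply is that 0.79 is a cautious planning figure. It lies inside the 0.69 to 0.83 range spanned by the possible p-value rules, and under the exact test it understates power. Cohort 4 has the same 12 + 3 as every other cohort, and 9.4.2 powers the study on single-copy-assay change in Cohorts 1-3, so no sample size or decision rule rests on it. This stands, and it limits the severity.

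Four stronger readings are tempting, and the documents do not support them.
- A reader might infer that 0.79 and 0.38 come from two different calculations, or that 0.79 is an arithmetic slip. A single truncated-size t-test (10 v 2 and 32 v 8) roughly fits both. The origin is unstated, so neither account is proven.
- A reader might infer that Cohort 4's power is overstated. Under the exact test the opposite holds; only the t approximation falls below 80% at 0.79.
- A reader might infer that the stated power depends on using the exact test. It does not: the uncorrected normal test has the same rejection region without ties, and the corrected one still exceeds 80% at 0.79. What does depend on the rule is a claim of 80% at about 0.70.
- A reader might take 0.70 as simply the right number. It is right only for the exact test with SD 0.33, and that SD was given for resting CD4+ T-cells. The Cohort 4 endpoint is in PBMCs, with imputation below the limit that can create ties.

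It can also be said that revising a planning figure this late changes little. That is fair for the figure itself but not for the p-value rule, which still governs how the results are tested.

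**Conclusion.** The point holds in a limited form. Confidence is high that 0.79 is not the 80% point of the test named in 9.4.2, whichever p-value rule is used, and low on how it arose. Under the exact test the figure is conservative, by about 9 points of power or 0.10 log10 (0.79 − 0.69).

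The open p-value rule in SAP 7.13 is the more useful part. Relative to the exact test at 0.79, the continuity-corrected normal loses about 5 points of power (88.9 − 83.5) and the continuity-corrected t about 13 (88.9 − 75.7). A result at U = 4 would be significant under one rule and not under another. Severity is minor to moderate. The numbers rest on a normal shift, no ties and SD 0.33 applying to PBMCs.

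**What to change.** In Protocol 9.4.2, restate the Cohort 4 figure for the test to be used. For the exact test that is about 0.70 log10 at 80% power, or 0.79 at about 89%. If 0.79 at 80% is kept, state the method behind it. Add that SD 0.33 comes from resting CD4+ T-cells and is assumed to apply to PBMCs.

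In SAP 7.13.1 and 7.13.2, specify exact permutation p-values for the 12 v 3 rank-sum comparison, with mid-ranks for ties, and Hodges-Lehmann intervals from the matching exact distribution. Settle this before the treatment comparison is run.

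The cost is one figure and a caveat in the protocol and a sentence in the SAP. No participants, samples or change in sample size are needed.
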